4.2. Scientific Rationale for Study Design

Cyclin-dependent kinase 4/6 inhibition has been demonstrated nonclinically to synergize with anti-estrogen therapy in breast cancer models, and subsequent clinical work has led to the FDA approval of 3 CDK4/6 inhibitors (palbociclib, ribociclib, and abemaciclib) in both 1L and 2L mBC.

CDK4/6 inhibitors are associated with known AEs. The purpose of this study is to better identify those AEs in participants with 1L and 2L mBC. Efficacy measurements will also be collected.

4.3. Justification for Dose

G1T38-02 was a Phase 1/2 study consisting of 2 parts: a dose-escalation phase (Phase 1) and a dose-expansion phase (Phase 2) of lerociclib in combination with fulvestrant in women with 2L HR+/HER2- mBC. A total of 110 female participants received lerociclib across doses of 200 mg to 650 mg QD and 100 mg to 250 mg BID.

The selected dose of lerociclib 150 mg BID demonstrated an improved tolerability profile relative to QD dosing and to all other BID doses, including improved rates of gastrointestinal AEs as well as lower rates of neutropenia.

Best overall response was comparable between the 150-mg BID dosing group and the 200-mg BID dosing group (CBR of 73.7% versus 70.7%). As such, 150 mg BID lerociclib was selected as the recommended dose.

Notably, of the participants treated with lerociclib 150 mg BID, Grade 4 neutropenia was reported in 1 participant, and no other lerociclib-related Grade 4 AEs were reported at that dose level. Grade 3 febrile neutropenia was also reported in 1 participant treated with lerociclib 150 mg BID. The most common Grade 3/4 AEs in participants treated with 150 mg BID were neutropenia (40%), leukopenia (20%), and lymphopenia (10%).

No lerociclib dose interruptions or reductions were required in any participant who experienced Grade 3 neutropenia without fever.

No lerociclib-related nausea, vomiting, or diarrhea event of Grade 3 or higher severity was reported in any participant treated with 150 mg BID.

Grade 2 stomatitis was reported in 1 participant treated with 150 mg BID. Grade 1 alopecia was reported in 1 participant treated with lerociclib 150 mg BID; this was the only alopecia event in the study.

The only lerociclib-related SAE reported in the 150-mg BID cohort was an episode of Grade 2 pneumonitis, which resolved with discontinuation of lerociclib. Lerociclib dose reduction occurred in 2 participants treated with 150 mg BID. No cases of QT prolongation or venous thromboembolism were reported at any dose level in the study.

4.4. End of Study Definition

The end of the overall study will be reached when all participants have ended their participation in the study. Participants may be eligible for a long-term extension study of lerociclib.

Additionally, the study may be placed on hold or terminated in any of the following circumstances:

- Overall, country-/region-specific, or site-specific study hold or termination by the Sponsor at any time, for any reason
- Study hold or termination in a specific country/region by the relevant Health Authority
- Study-site closure initiated by the IRB/IEC or by the Principal Investigator as detailed in Section [10.1.9.3](#)

Refer to Section [7.4](#) for additional information about potential study stoppage.

The Sponsor will notify the Investigators in the event of any study hold or termination, or in the event of overall study completion (defined as completion of the last study visit of the last participant in the study).

5. STUDY POPULATION

The study population will consist of female or male participants with newly diagnosed, treatment-naïve or post-first-line endocrine therapy HR+/HER2- mBC. All participants must be able to provide written consent and meet all of the study inclusion criteria and none of the study exclusion criteria.

Note: “Enrolled” in the context of a clinical study means the agreement of a participant to participate in a clinical study following completion of the informed consent process. Potential participants who are screened for the purpose of determining eligibility for the study, but do not participate in the study, are not considered enrolled.

Prospective approval of protocol deviations to recruitment and enrollment criteria, also known as protocol waivers or exemptions, is not permitted.

5.1. Inclusion Criteria

Prospective participants are eligible to be included in the study only if **all** of the following criteria apply:

Informed Consent

1. Is capable of giving signed informed consent as described in Section 10.1.3. This includes compliance with the requirements and restrictions listed in the study ICF and in this protocol.

Age

2. Must be at least 18 years of age, or the legal age of consent in the jurisdiction in which the study is taking place, at the time of giving signed informed consent.

Type of Participant and Disease Characteristics

3. Has a histologically and/or cytologically confirmed diagnosis of ER-positive and/or progesterone receptor-positive breast cancer by local laboratory.
4. Breast cancer is also HER2-negative and advanced (locoregionally recurrent; not amenable to curative therapy, eg, surgery and/or radiotherapy; or metastatic) and meets one of the following criteria:
 - Newly diagnosed advanced/metastatic breast cancer, treatment-naïve
 - Relapsed with documented evidence of relapse following neoadjuvant (adjuvant) endocrine therapy, with no treatment for advanced/metastatic disease
 - Relapsed with documented evidence of relapse following completion of adjuvant endocrine therapy, then subsequently progressed with documented evidence of progression after 1 line of endocrine therapy (with either tamoxifen or an AI) for advanced/metastatic disease
 - Newly diagnosed advanced/mBC at diagnosis that progressed with documented evidence of progression after 1 line of endocrine therapy (with either tamoxifen, exemestane, or an AI)
5. Eastern Cooperative Oncology Group performance status is 0 or 1

6. Has adequate bone marrow and organ function, as defined by all of the following laboratory values:
 - Absolute neutrophil count $\geq 1.5 \times 10^9/\text{L}$
 - Platelets $\geq 100 \times 10^9/\text{L}$
 - Hemoglobin $\geq 9.0 \text{ g/dL}$
 - International normalized ratio ≤ 1.5
 - Creatinine clearance $\geq 60/\text{mL}$, as estimated by Cockcroft-Gault equation
 - Alanine aminotransferase and AST below $2.5 \times \text{ULN}$
 - Total bilirubin $\leq 1.5 \times \text{ULN}$; OR, for participants with well-documented Gilbert's Syndrome, direct bilirubin within normal range of the central laboratory
7. Baseline QTc interval is $< 470 \text{ msec}$.
8. Is able to take/swallow oral medications.

Sex and Contraceptive/Barrier Requirements

9. Must meet all of the applicable requirements for pregnancy and contraception, as follows:
 - a. If female, is either:
 - A participant of childbearing potential (as defined in [Appendix 4](#)) who:
 - Has a negative pregnancy test result at Screening and Cycle 1 Day 1 (ie, prior to the first dose of any study intervention), as noted in the SoA ([Table 1](#));
 - Is not breastfeeding;
 - Agrees to use highly effective contraceptive measures (as defined in [Appendix 4](#)) from 28 days prior to the first dose of any study intervention through at least 365 days (1 year) following the last dose of any study intervention, and to align contraceptive use with the relevant prescribing information for fulvestrant and/or goserelin, as applicable (refer to [Appendix 4](#)); AND
 - Agrees not to donate ova from the first dose of any study intervention through at least 1 year following the last dose of any study intervention.
 - OR
 - A participant of nonchildbearing potential, as confirmed by meeting both of the following criteria:
 - Has a negative serum pregnancy test result prior to the first dose of any study intervention, AND
 - Is confirmed by the Investigator to be medically postmenopausal per one of the following parameters:
 - Age, in addition to one of the following:
 - Menses status (ie, absence of menses for $\geq 1 \text{ year}$)

- Surgical status (ie, prior hysterectomy or bilateral oophorectomy)
 - Follicle-stimulating hormone level
- b. If male:
- Agrees to use a highly effective method of contraception (eg, male condom in addition to hormonal contraception; refer to [Appendix 4](#)) during intercourse with a female partner of childbearing potential from 28 days prior to the first dose of any study intervention through at least 365 days (1 year) following the last dose of any study intervention, and to align contraceptive use with the relevant prescribing information for fulvestrant and/or goserelin, as applicable ([Appendix 4](#)); AND
 - Agrees to refrain from donating sperm from the first dose of any study intervention through 1 year following the last dose of any study intervention.

Note: For all study participants, contraceptive use must be consistent with local regulations regarding the methods of contraception for those participating in clinical studies. Refer to [Appendix 4](#) for additional guidance.

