| FSH Measurement (Female Participants of Non-Childbearing Potential Only) | X | | | | | | | | |
| 12-Lead ECG ^e | X ^b | X | X | X | X | X (at Cycles 4 and 5 only) | X | | |
| ECHO or MUGA with EF | | As clinically indicated by Investigator | | | | | | | |
| Vital Signs | X | X | X | X | X | X | X | | |
| PK Sampling ^f | | X | X | X | X | X (at Cycles 4 and 5 only) | | | |
| Tumor Evaluation (per RECIST v1.1) | X | Every 8 weeks (± 7 days) during the first 12 months and every 12 weeks (± 7 days) thereafter until disease progression, death, withdrawal of consent, loss to follow-up, or participant/legally acceptable representative decision, and at EOT/ED (as applicable). If PR/CR is reported, confirmation of response is required; confirmatory assessment should be performed ≥ 4 weeks after response is first documented. ¹ | | | | | | | |
| Whole-Body Bone Scan ^g | X | Every 8 weeks (± 7 days) for the first 12 months, then: -If initial bone scan is positive for bony lesion, every 12 weeks thereafter, OR -If initial bone scan is negative for bony lesion, bone scan can be done annually or per Investigator standard of care. | | | | | | | |

| Procedure | Screening | Treatment Phase | | | | | | Post-Treatment Follow-up Phase | |
|---|--|--|--|----------|----------|-------------------|--|-----------------------------------|--------------------------|
| | | Cycle 1 | | Cycle 2 | Cycle 3 | Subsequent Cycles | EOT/ED (as applicable) | Safety Follow-up | Survival Follow-up Phase |
| Study Day(s) | D-42 to D-1 | D1 | D15 | D1 | D1 | D1 | Within 15 days after last dose of lerociclib | Last dose of lerociclib + 30 days | Every 12 weeks |
| Visit Window (days) | - | - | ± 2 days | ± 2 days | ± 2 days | ± 2 days | - | + 5 days | ± 7 days |
| Lerociclib Administration/Accountability | | Twice daily continuously in 28-day cycles ^a | | | | | | | |
| Letrozole Administration ⁱ | | Once daily continuously in 28-day cycles | | | | | | | |
| Fulvestrant Administration ⁱ | | X | X | X | X | X | | | |
| Goserelin Administration ^j | X (goserelin dosing required for ≥ 28 days prior to study entry) | X (determined as date of participant's last goserelin dose + 28 days ^l) | q28d after goserelin C1D1 for the individual participant | | | | | | |
| AE/SAE Review | X (continuous from Screening through 30 days after last study intervention dose) | | | | | | | | |

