4. STUDY DESIGN

4.1. Overall Design

This is a multicenter, single-arm, open-label study to evaluate the safety and efficacy of lerociclib administered in combination with standard endocrine therapy in female or male participants with HR+/HER2- mBC.

The study population will consist of newly diagnosed, treatment-naïve participants with HR+/HER2- mBC (collectively referred to as the first-line, or 1L, population) and participants with HR+/HER2- mBC who have already progressed on first-line endocrine therapy such as tamoxifen, anastrozole, or letrozole (collectively referred to as the second-line, or 2L, population).

Approximately 100 participants will be enrolled and dosed in the study, with approximately 50 participants enrolled and dosed for each line of therapy (1L or 2L). All premenopausal or perimenopausal female participants, and all male participants, must be receiving goserelin for at least 28 days prior to entering the study and will remain on goserelin throughout the study, in accordance with the prescribing information and according to the study site's standard practice. The schedule for administration of goserelin for each individual participant is decoupled from the rest of the study visit schedule, and will be determined by the date of the participant's most recent dose of goserelin at the time of study entry (with "goserelin C1D1" defined as the date of the participant's most recent dose + 28 days, then every 28 days subsequently).

All study participants (1L and 2L populations) will receive the Investigator's choice of AI (letrozole) or fulvestrant plus lerociclib 150 mg BID. All participants should be treated according to the best current practice guidelines and standard of care within each institution or country where the study is conducted.

The study will consist of 3 phases: a Screening Phase of up to 42 days in duration; a Treatment Phase (which includes a Safety Follow-up Visit occurring 30 days after the last dose of lerociclib); and a Post-Treatment Follow-up Phase (which includes a Survival Follow-up Phase) that will continue until death, loss of follow-up, withdrawal of consent, or the end of the study (whichever occurs first).

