10.4. Appendix 4: Contraceptive and Barrier Guidance

10.4.1. Definitions

Study participants in the following categories are considered **female participants of childbearing potential (fertile/of reproductive potential)**:

1. Following menarche.
2. From the time of menarche until becoming **postmenopausal**, unless **permanently sterile** (see below).
 - A postmenopausal state is defined as no menses for 12 months without an alternative medical cause.
 - A high FSH level in the postmenopausal range may be used to confirm a postmenopausal state in female participants not using hormonal contraception or HRT. However, in the absence of 12 months of amenorrhea, confirmation with more than 1 FSH measurement is required.
 - Female participants on HRT and whose menopausal status is in doubt will be required to use one of the non-estrogen hormonal highly effective contraception methods if they wish to continue their HRT during the study. Otherwise, they must discontinue HRT to allow confirmation of postmenopausal status before study enrollment.
 - **Permanent sterilization** methods (for the purposes of this study) are defined as the following:
 - Documented hysterectomy
 - Documented bilateral salpingectomy
 - Documented bilateral oophorectomy

For individuals with permanent infertility due to an alternate medical cause other than the above, (eg, Mullerian agenesis, androgen insensitivity, gonadal dysgenesis), Investigator discretion should be applied to determining study entry.

Notes:

- Documentation can come from the site personnel's review of the participant's medical records, medical examination, or medical history interview.
- If fertility is unclear (eg, amenorrhea in adolescents or athletes) and a menstrual cycle cannot be confirmed before the first dose of study intervention, additional evaluation should be considered.

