4.10.1.5 Examination of Subgroups

The uniformity of the treatment effect for the efficacy analysis of Progression-Free Survival (PFS) will be examined for the following subgroups:

1. Age at Enrollment
2. Ethnicity (Not Hispanic or Latino, Other)
3. Race (White, Other)
4. Sex (Female, Male) – While males are allowed in the study it is expected that their enrollment will be very limited. The CSR will note any occurrences when the enrollment of males is too low to allow analyses to run.
5. Childbearing Potential (Yes, No)
6. For Non-Childbearing Potential (Premenarchal, Surgically Sterile, Postmenopausal, Other)
7. Geographic Region
8. Age at Initial Diagnosis
9. Stage at Initial Diagnosis
10. Age at Most Recent Diagnosis
11. Metastasis Sites (Nervous System, Bone, Liver, Respiratory System, Adrenal Gland, Brain, Breast, Other) – may be categorized
12. Histology (Epithelial of ductal origin, Epithelial of lobular origin, Other)
13. Initial Cancer Type [Ductal carcinoma in situ (DCIS), Lobular carcinoma in situ, Invasive ductal carcinoma (ductal breast cancer), Invasive lobular carcinoma, Medullary carcinoma, Mucinous (colloid) carcinoma, Tubular carcinoma, Papillary carcinoma, Metaplastic breast cancer (mBC), Phyllodes tumors, Mammary Paget disease (MPD), Inflammatory breast cancer] – may be categorized
14. Stage at Study Enrollment
15. Reason for Discontinuation of Most Recent Prior Therapy (Progressive Disease, Toxicity, Completion, Unknown, Other, Specify)

Summaries of PFS by line of therapy and subgroup will be produced. No formal statistical analysis will be performed within subgroup.

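### Criterion 9a in Protocol 5.1 and Appendix 4 sort women into postmenopausal and non-childbearing categories by different rules, and neither is named as the rule for the goserelin requirement

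*Protocol*

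**What the plan says.** Criterion 9 in Protocol 5.1 opens with its purpose: "Must meet all of the applicable requirements for pregnancy and contraception, as follows". A woman enters through one of two arms. The childbearing arm takes its definition from Appendix 4. The non-childbearing arm uses its own list. It needs a negative serum pregnancy test and the condition "Is confirmed by the Investigator to be medically postmenopausal per one of the following parameters". The parameters are age together with one of absence of menses for a year or more, "Surgical status (ie, prior hysterectomy or bilateral oophorectomy"), or FSH level. No age threshold, FSH range or number of FSH values is given.

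Appendix 4 (10.4.1) says "A postmenopausal state is defined as no menses for 12 months without an alternative medical cause". It allows a high FSH in the postmenopausal range as confirmation, but "in the absence of 12 months of amenorrhea, confirmation with more than 1 FSH measurement is required". Hysterectomy, bilateral salpingectomy and bilateral oophorectomy appear under a separate route, permanent sterilization.

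The Schedule of Activities (Table 1) has one FSH row, marked at Screening: "FSH Measurement (Female Participants of Non-Childbearing Potential Only"). Table 9 offers FSH and estradiol as needed in the same group. The schedule in SAP 6.1 gives the FSH row for all female participants.

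On goserelin, Protocol 4.1 says "All premenopausal or perimenopausal female participants, and all male participants, must be receiving goserelin for at least 28 days prior to entering the study"; the synopsis, 6.1 and footnote j of Table 1 repeat it. None of these places defines premenopausal or perimenopausal, or points to 5.1 or Appendix 4.

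SAP 4.10.1.5 lists PFS subgroups by childbearing potential and, within it, "For Non-Childbearing Potential (Premenarchal, Surgically Sterile, Postmenopausal, Other").

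**The concern.** The two arms of one either/or criterion rest on different definitions, so they need not divide women cleanly. Some women can qualify for both arms and some may qualify for neither. Two things depend on the class.

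- **Pregnancy protection.** A woman of childbearing potential must use highly effective contraception from 28 days before the first dose until at least 365 days after the last, and is tested on Day 1 of every cycle (5.1, Table 1 footnote d, 8.2.5). A woman in the other arm has one negative serum test before dosing. The amendment summary explains the added testing by the absence of reproductive and developmental toxicity studies, so this is the risk the current version set out to control.
- **Eligibility.** Sections 5 and 8 bar waivers, so a site cannot resolve a woman who fits neither arm by exception.

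A third matter is separate. Menopausal status decides who must be on goserelin, and the protocol names no definition for that purpose.

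**Working it through.** No formula applies and the plan gives no figure to reproduce. The check is to take each kind of patient through both definitions.

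| Patient | 5.1, non-childbearing arm | Appendix 4 | Result |
|---|---|---|---|
| A year or more without menses, caused by treatment | Meets the menses item, which has no exclusion for cause | Not postmenopausal on this basis; not sterilized; so of childbearing potential | Can satisfy both arms |
| Menstruating, bilateral salpingectomy | Menses item not met; salpingectomy not among the surgical items; only the FSH item is left | Permanently sterile, so outside the childbearing class | May satisfy neither arm |
| Fewer than 12 months without menses, one FSH value | FSH item names no range and no number of values | Needs a value in the postmenopausal range and more than one measurement | Class depends on which section the site reads |
| Hysterectomy, ovaries retained | Meets the surgical item, labelled postmenopausal | Permanently sterile, a category separate from menopause | Non-childbearing in both; only the menopausal label differs |

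Each 5.1 entry also needs the age condition and the Investigator's confirmation.

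**Can the first patient enroll?** Yes. Exclusion 7 exempts neoadjuvant and adjuvant chemotherapy, and 4.1 sets 28 days as a minimum for prior goserelin, not a maximum.

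**Does the class change what is done to her?** Yes. Table 1 footnote d and 8.2.5 use the Appendix 4 definition for per-cycle testing, while 5.1 allows her to be admitted as non-childbearing, without the contraception undertaking.

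**Does the schedule support the rules?** Only in part. The FSH row and Table 9 restrict the test to women already classed as non-childbearing, although FSH is one of the items that decides the class. The SAP schedule has a different population for the same row, although SAP section 1 names Protocol Version 3.0 as its basis.

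**Does 5.1 decide goserelin?** No text says so. The requirement stands by itself in the synopsis, 4.1, 6.1 and footnote j. Criterion 9a is, however, the eligibility text in which an Investigator confirms menopausal status. For the hysterectomy patient it would yield postmenopausal, whereas Appendix 4 would not on that ground.

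**The case against.** A reader might infer something stronger: that women with functioning ovaries will be treated as postmenopausal, given letrozole without goserelin, and so distort response and PFS. The documents do not support that. Criterion 9a concerns pregnancy and contraception. Goserelin is required of all premenopausal and perimenopausal women in its own right, under the prescribing information and site practice, and 4.1 also asks for treatment by current guidelines. The step from 9a to goserelin is an inference about how a site might read the protocol. The documents also give no basis for estimating how many women would be affected or by how much ORR or PFS would move.

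Other parts of the defense also stand:

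- For contraception and pregnancy testing, hysterectomy causes no conflict, because both sections make the woman non-childbearing.
- Section 5.1 does not say that one FSH value is enough. That is inferred from its silence and the single scheduled measurement.
- The absence of a numeric FSH cut-off is not a contradiction, since Appendix 4 has none either. The difference lies in the range wording and the number of measurements.
- A repeat FSH is already possible. Screening lasts up to 42 days, and Appendix 2 allows additional tests at any time.
- The SAP has separate categories for surgically sterile and postmenopausal women, so a correct place exists for each, and the subgroup summaries are descriptive.
- Age and Investigator confirmation are safeguards, though age has no threshold and adults from 18 can enter.

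None of this removes the overlap for treatment-induced amenorrhea or the gap for salpingectomy. Those follow from the wording alone.

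**Conclusion.** The inconsistency is in the text. Section 5.1 and Appendix 4 define postmenopausal and non-childbearing status differently, and two outcomes follow without any inference about goserelin. A woman with treatment-induced amenorrhea can be non-childbearing in one place and of childbearing potential in the other. A menstruating woman with bilateral salpingectomy may fit neither arm unless her FSH qualifies her.

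That no definition governs the goserelin requirement is also a fact of the documents. That a site would use a hysterectomy-based 9a confirmation to set the requirement aside is possible but not stated, and should be reported only as a risk of misreading.

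On size, the number of women concerned cannot be derived from the documents. The planned 50 or so per line and the ORR precision statement do not depend on this point, and neither do the other analysis figures. SAP tables by childbearing potential would inherit any inconsistent classing, but they carry no formal analysis. This is a clarification worth making for participant protection and consistent eligibility, not a defect in the statistical design.

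**What to change.** Reconcile criterion 9a, Appendix 4 (10.4.1), the FSH row of Table 1, Table 9 and the schedule in SAP 6.1 so that every woman falls in exactly one category. In particular:

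- State menopausal status, which is used for goserelin, separately from childbearing potential, which is used for contraception and pregnancy testing.
- Say in 4.1 and 6.1 which definition governs the goserelin requirement.
- Align the FSH row, its population and the number of measurements with whichever rule is adopted, and carry the same row into the SAP.
- Record the basis for menopausal status on the eCRF if it is not already captured. The SAP's reason categories suggest that part of it may be.

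Which clinical definition applies, and whether there is an FSH threshold, is for the sponsor's medical team to decide.

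The cost is amendment wording, a matching edit to the SAP schedule and at most one eCRF field. FSH and estradiol are already in Table 9, so no new laboratory test is needed. A repeat FSH would add burden only where the adopted rule calls for one, and Appendix 4 already does so in some women.
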